#### **10.1.2.2 Vaccination**

Once all pre-vaccination procedures have been completed and subject eligibility determined, the study vaccine will be administered (on Day 0) IM into the deltoid muscle of the non-dominant (if possible) arm. A 25 gauge needle of one inch or 2.5 cm in length should be used for vaccination for subjects with a BMI under 35; for subjects with a BMI of 35 and over, the use of a 25 gauge needle (when available) of 1.5 inches or 3.8 cm in length is required to reach the muscle. For subjects with BMI greater than or equal to 35, if the longer 25 gauge needle is not available, then a long 23 gauge needle (1.5 inches; 3.8 cm) can be used. In order to prevent possible confounding of vaccination site reactions, whenever possible, blood samples will not be collected from the same arm as the one used for vaccination. The arms used, both for blood collection and vaccination, will be documented in the source documents.

#### **10.1.2.3 Fifteen Minutes Post-vaccination**

The following safety observation procedures will be performed for all subjects immediately following study vaccine administration:

- Subjects will remain in the clinic for at least 15 minutes post-vaccination for observation. The observation period will include an assessment of immediate solicited local and systemic reactions. Any unusual signs or symptoms reported during the initial 15 minutes post-vaccination will result in continued close monitoring. Based on their condition,

subjects may be asked to remain in the clinic for their safety for more than 15 minutes after vaccination (the reason will be recorded in the source documents). All data (including the assessment of solicited local and systemic reactions) will be recorded in the source documents during and after the observation period. Refer to Section 10.3.1 for details regarding the assessment of AEs and/or solicited local and systemic reactions;

- During the observation period, subjects will be provided with a measurement device template for measuring (in mm) solicited local reactions of erythema (redness) and swelling and an oral digital thermometer for recording daily temperature (in degrees Celsius or Fahrenheit). Subjects will be shown how to enter their data in their eDiary. Each subject will be provided with the following instructions on the measurements they are to make:
  - How to collect his/her OT in degrees Celsius or Fahrenheit with the provided digital thermometer;
  - From the evening of Day 0 to the evening of Day 7, the subject will measure his/her OT at approximately the same time each evening and will record the results;
  - The OT should not be collected immediately following consumption of a hot or cold beverage or after smoking.
  - The subject is to also take his/her OT if he/she feels feverish and to record the highest temperature of the day. In the event that a temperature  $\geq 38.0^{\circ}\text{C}$  or  $\geq 100.4^{\circ}\text{F}$  is obtained, the subject will be allowed to take over-the-counter antipyretics (e.g. acetaminophen/paracetamol, aspirin, naproxen, or ibuprofen) and will be advised to increase the frequency of OT measurements to approximately every four hours, until he/she is no longer febrile (fever is defined as a temperature of  $\geq 38.0^{\circ}\text{C}$  or  $\geq 100.4^{\circ}\text{F}$ ). The subject is to document medication intake, which will be reviewed by the site personnel;
- How to measure any solicited local reactions, including erythema (redness) and swelling diameter at the injection site using the measurement template supplied for this purpose; subjects will also be requested to evaluate pain at the injection site. Local reactions will be assessed every day starting in the evening of Day 0 and up to the evening of Day 7 and the results will be recorded. The severity of solicited local reactions will be graded according to the Food and Drug Administration (FDA) Guidance for Industry: Toxicity Grading Scale for Healthy Adult and Adolescent Volunteers Enrolled in Preventive Vaccine Clinical Trials (FDA, 2007), as presented in [Table 6](#).
- How to grade, on a daily basis from the evening of Day 0 through to the evening of Day 7, each of the solicited systemic reactions and their severity (as per the same guidance used for solicited local reactions; see [Table 6](#)) (FDA, 2007) and to record the worst grade of the day for each of these solicited systemic reaction. The instructions will include how to examine and grade swelling in the neck and axilla and to record any unusual feeling and/or swelling;
- Subjects will be advised that they will be asked about the occurrence of any symptoms or events requiring medical attention and the use of any concomitant medication during the 21-day post-vaccination period and until the end of the surveillance period;

Confidential Information

- Subjects will be instructed to contact the clinical site for any unsolicited AEs and/or solicited local and systemic reactions of greater than Grade 2 (moderate). Based on their condition, the Investigator may request that the subject return to the clinic for evaluation;
- Subjects will be advised on emergency contact information and instructions for contacting study personnel. Subjects will be advised to immediately contact the Investigator (or his/her designee) in the event of an SAE or a medical emergency. Subjects will be provided with a phone contact number and be instructed to call if any suspected reaction to the vaccination is felt to be significant or of concern;
- Subjects will be advised to notify their health care professional(s) (e.g. primary care physician) that they are participating in a clinical research study of an influenza vaccine;
- After the 15-minute observation period (allowed window of + 15 minutes) is completed, measure vital signs (BP, HR, and OT) as described in Section 10.3.1.4. Any out-of-range measurements will be assessed by the Investigator (or his/her designee) and any further action will be determined upon his/her medical decision;
- Instruct the subjects to perform measurements of local and systemic reactions at approximately the same time each day from Day 0 to Day 7 (preferably in the evening);
- Provide appointments (date and time) for the next planned visit to the clinical site (Day 21) and also for the Days 1 and 8 phone contacts and passive and active surveillance periods;
- The subject will be released from the clinical site once all Day 0 post-vaccination procedures have been completed and the subject is in stable condition.

### 10.1.3 Day 1 and Day 8 (Telephone Contact)

The following procedures will be performed during the phone contact (acceptable interval of + 1 day for Day 1 and  $\pm$  1 day for Day 8):

- Ask the subjects about any difficulties in recording their data, any change in health, any visits to health care facilities and/or medical practitioners, and any use of concomitant medications. Record the information in the source documents;
- For any unsolicited AEs and/or solicited local and systemic reactions of greater than Grade 2 (moderate), the Investigator should be informed within 48 hours of the time the clinical site is made aware of the event. The Investigator may request that the subject return to the clinic for evaluation;
- Advise subjects to immediately contact the Investigator (or his/her designee) in the event of any AE that requires medical attention. Subjects will be provided with a phone contact number and be instructed to call if any suspected reaction to the vaccination is felt to be significant or of concern;
- Remind the subjects how to measure and record any solicited local and systemic reactions. Subjects should also be reminded to record any changes in health, including changes in AEs and changes in medications;

- Remind subjects to immediately report any new or a worsening respiratory illness, as defined in Section 10.2.1. Ensure that subjects have the reminder aid listing the respiratory illness symptoms and contact information for the study site;
- Remind subjects to immediately report any symptoms that meet the definition of an ILI, as defined in Section 10.2.1. Ensure that subjects have the reminder aid listing the symptoms of ILI and contact information for the study site;
- Remind subjects of their next appointment (date and time) for the clinical visit and/or the next phone contact. Subjects will also be reminded to record their data in the electronic system in a timely manner.

In the event that a subject cannot be reached via phone, he/she may be contacted by text message or via email (if these contacts are available). However, the phone should be the initial and preferred means of communication.

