### **5 STUDY POPULATION**

#### **5.1 Inclusion Criteria**

Subjects must meet all of the following inclusion criteria to be eligible for participation in this study; no protocol waivers are allowed:

1. Subjects must have read, understood, and signed the informed consent form (ICF) prior to participating in the study; subjects must also complete study-related procedures and communicate with the study staff at visits and by phone during the study;
2. Subject must have a body mass index (BMI) below 40 kg/m^2;
3. Subjects are considered by the Investigator to be reliable and likely to cooperate with the assessment procedures and be available for the duration of the study;
4. Male and female subjects must be 18 to 64 (has not yet had his/her 65th birthday) years of age, inclusive, at the Screening/Vaccination visit (Visit 1);
5. Subjects must be in good general health prior to study participation, with no clinically relevant abnormalities that could jeopardize subject safety or interfere with study assessments, as assessed by the Principal Investigator or sub-Investigator (thereafter

referred as Investigator) and determined by medical history, physical examination, and vital signs;

Note: Subjects with a pre-existing chronic disease will be allowed to participate if the disease is stable and, according to the Investigator's judgment, the condition is unlikely to confound the results of the study or pose additional risk to the subject by participating in the study. Stable disease is generally defined as no new onset or exacerbation of pre-existing chronic disease three months prior to vaccination. Based on the Investigator's judgment, a subject with more recent stabilization of a disease could also be eligible.

6. Female subjects must have a negative urine pregnancy test result at the Screening/Vaccination visit (Visit 1);
7. Female subjects of childbearing potential must use an acceptable method of birth control, as defined in Appendix 4 (Section 19.4);
8. Non-childbearing females are defined as:
  - Surgically-sterile (defined as bilateral tubal ligation, hysterectomy or bilateral oophorectomy performed more than one month prior to vaccination); or
  - Post-menopausal (absence of menses for 24 consecutive months and age consistent with natural cessation of ovulation).

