### **10.1.2 Screening/Vaccination (Visit 1)**

Emergency equipment must be available on site and appropriate treatment must be instituted as soon as possible in the event of anaphylaxis or any other immediate hypersensitivity reaction. The Investigator will be on-site on vaccine administration days and for the duration of the observation period for the last subject dosed on that day. The Investigator will be available on call for the remainder of the study. A physician should be immediately available at the clinical site to administer treatment or to apply procedures for any immediate AEs/SAEs.

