**Table 6 Severity Grades for Solicited Local and Systemic Reactions**

Symptoms	Severity				
	None	Grade 1 (Mild)	Grade 2 (Moderate)	Grade 3 (Severe)	Grade 4 (Potentially life-threatening)
Injection Site Reactions (Local Reactions)					
Erythema (redness)	< 25 mm	25 - 50 mm	51 - 100 mm	> 100 mm	Necrosis or exfoliative dermatitis
Swelling	< 25 mm	25 - 50 mm and does not interfere with activity	51 - 100 mm or interferes with activity	> 100 mm or prevents daily activity	Necrosis
Pain	None	Does not interfere with activity	Repeated use of non-narcotic pain reliever for more than 24 hours or interferes with activity	Any use of narcotic pain reliever or prevents daily activity	Results in a visit to emergency room (ER) or hospitalization
Solicited Systemic Reactions					
Fever (°C or °F)	< 38.0 °C < 100.4 °F	38.0 - 38.4 °C 100.4 - 101.1 °F	38.5 - 38.9 °C 101.2 - 102.0 °F	39.0 - 40.0 °C 102.1 - 104.0 °F	> 40.0 °C > 104.0 °F

Confidential Information

Symptoms	Severity				
	None	Grade 1 (Mild)	Grade 2 (Moderate)	Grade 3 (Severe)	Grade 4 (Potentially life-threatening)
Headache	None	No interference with activity	Repeated use of non-narcotic pain reliever for more than 24 hours or some interference with activity	Significant; any use of narcotic pain reliever or prevents daily activity	Results in a visit to emergency room (ER) or hospitalization
Fatigue	None	No interference with activity	Some interference with activity	Significant; prevents daily activity	Results in a visit to emergency room (ER) or hospitalization
Muscle aches	None	No interference with activity	Some interference with activity	Significant; prevents daily activity	Results in a visit to emergency room (ER) or hospitalization
Joint aches, chills, feeling of general discomfort or uneasiness (malaise), swelling in the axilla, swelling in the neck	None	No interference with activity	Some interference with activity not requiring medical intervention	Prevents daily activity and requires medical intervention	Results in a visit to emergency room (ER) or hospitalization

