#### **13.1.6 Initial SAE Reporting by the Investigator**

SAEs related to pre-treatment study procedures will be reported from the time the ICF is signed. All post-vaccination SAEs (treatment-emergent SAEs) will be reported from the time of receiving the study vaccine on Day 0 through to the end of the surveillance period (final scheduled phone contact). The Investigator (or designee) must report, by phone or email, all SAEs, whether considered related to the study vaccine or not, and whether considered unexpected or expected (as defined in Section 13.1.1), to Medicago (or its designee) within 24 hours of the Investigator learning of the event. The Investigator must also complete the AE screen of the eCRF page for SAE reporting. If the eCRF is not available, the Investigator must use a paper SAE report form, and send, via e-mail, a copy to the Medicago safety e-mail address and the appropriate regional (Americas or EU/APAC) e-mail address:

Medicago Safety e-mail address: [contact]  
Americas SAE e-mail address: **CCI** [REDACTED]

---

Confidential Information

EU/APAC SAE e-mail address:

CCI

Sponsor Safety Contact:

PPD

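### Day 1 and Day 8 calls: a 48-hour allowance for telling the Investigator has no exception for Grade 4 or serious events, so an SAE could take 72 hours to reach the sponsor

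*Protocol*

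**What the plan says.** Protocol 10.1.3 covers the Day 1 and Day 8 telephone calls. Staff ask about changes in health and about "any visits to health care facilities and/or medical practitioners". For unsolicited AEs and solicited reactions above Grade 2, "the Investigator should be informed within 48 hours of the time the clinical site is made aware of the event", and the Investigator may then ask the subject to come back to the clinic. Nothing separates Grade 4 from Grade 3, or serious from non-serious events.

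The term Investigator is fixed in 5.1, inclusion criterion 5: eligibility is "as assessed by the Principal Investigator or sub-Investigator (thereafter" called simply the Investigator. Other site staff are not included.

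Protocol 13.1.6 requires all SAEs to be reported to the sponsor "within 24 hours of the Investigator learning of the event". A designee may make the report, but the stated starting point is the Investigator's knowledge. Under 13.1.10, the SUSAR limits of 7 days (deaths) and 15 days (other SAEs) run from first receipt by the sponsor or its designee.

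Three passages work in the other direction. At Day 0 (10.1.2.3): "Subjects will be advised to immediately contact the Investigator (or his/her designee) in the event of an SAE or a medical emergency". On the calls themselves (10.1.3): "Advise subjects to immediately contact the Investigator (or his/her designee) in the event of any AE that requires medical attention". And in 10.1.2: "The Investigator will be available on call for the remainder of the study". The SAP does not address the point.

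**The concern.** The calls are designed to bring out visits to emergency rooms and hospitals. In Table 6, a reaction that "Results in a visit to emergency room (ER) or hospitalization" is Grade 4 for pain and for every solicited systemic reaction except fever. For AEs in general, 13.1.2 describes Grade 4 as probably life-threatening unless treated promptly. A 48-hour allowance before an Investigator hears of such an event does not fit that definition.

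Two things wait during the delay. The Investigator cannot decide whether to recall the subject or assess causality. If the event is an SAE, the sponsor's receipt is also postponed, and with it the start of the SUSAR limits. The protocol itself treats severe hypersensitivity as an important potential risk (1.3.1, 13.1.3), and Day 1 is the first scheduled contact after an observation period of at least 15 minutes.

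The stake is subject safety and the timeliness of safety reporting. No estimate, error rate or analysis set is involved.

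**Working it through.** The plan gives no total for the time from site awareness to sponsor, so there is no stated figure to reproduce. The check adds the written maximum intervals.

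**Inputs**
- Site awareness to Investigator, on these two calls: up to 48 h (10.1.3).
- Investigator's learning to sponsor, for an SAE: up to 24 h (13.1.6).
- Sponsor's receipt to regulator, for a SUSAR: up to 7 days for deaths and 15 days for other SAEs (13.1.10).

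**Case 1: SAE first heard by staff who are not Investigators**
- As written: 48 h + 24 h = 72 h = 3 days.
- Investigator told at once: 0 h + 24 h = 24 h.
- 24 h counted from awareness by any site staff: at most 24 h = 1 day.
- Difference: 72 h − 24 h = 48 h.

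**Case 2: the same SAE is a SUSAR (outer limit from site awareness to regulator)**

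| | As written | With the change |
|---|---|---|
| Death | 3 + 7 = 10 days | 1 + 7 = 8 days |
| Other SAE | 3 + 15 = 18 days | 1 + 15 = 16 days |

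**Case 3: Grade 4 but not an SAE**

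Grade 4 and SAE are separate classes. Table 6 grades a reaction with an emergency room visit alone as 4, but 13.1.1 requires inpatient hospitalization of at least 24 hours or another listed criterion. For such an event no sponsor limit applies, and the only delay is to the Investigator: up to 48 h as written, same day with the change.

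**Does other text shorten the 48 hours?** The instructions in 10.1.2.3 and 10.1.3 to make contact immediately are addressed to subjects. They also allow contact with a designee, who need not be an Investigator. The on-call provision in 10.1.2 makes quick escalation possible but does not require it. No other section of either document sets a faster route from staff to Investigator.

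**Ambiguity in the sentence.** The Grade 2 threshold in 10.1.3 may qualify only the solicited reactions. The 48 hours would then cover unsolicited AEs of any grade, and 72 h still follows. If the threshold qualifies both kinds of event, an SAE graded 2 or lower has no stated staff-to-Investigator limit at all.

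**The case against.** The sentence in 10.1.3 is about severity, uses weaker language than 13.1.6, and never mentions SAEs. On an ordinary reading, the specific and mandatory section governs SAEs. The 48 hours is an upper limit that does not stop anyone from acting sooner, and the later contacts (10.1.4 to 10.1.6) set no staff-to-Investigator limit at all. If the person on the call is the designee, and the designee's awareness counts as the Investigator's, the maximum is 24 h. A subject who reports a hospital visit has already received care. Serious events were few in earlier studies: 21 SAEs among 1,793 recipients (21/1,793 = 1.2 %), none judged related (1.3, 1.3.1). The Study Procedures Manual, which is not available here, may set a faster route.

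Much of this stands. The two sections do not contradict each other, no written deadline is broken, the worst case should be uncommon, and the manual could close the gap. It is also true that moving the starting point in 13.1.6 would by itself cap SAE reporting at 24 h, and would do so for the later contacts too.

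Three points remain. First, 13.1.6 governs the step after the Investigator learns of the event; allowing a designee to report does not move that starting point. Second, a change to 13.1.6 alone would not reach Grade 4 events that are not SAEs. Third, care already received does not remove the need for a prompt decision by the Investigator on recall and causality.

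**Conclusion.** The concern holds as a worst case within the written rules. An SAE first heard on a Day 1 or Day 8 call by staff who are not Investigators may reach the sponsor 72 hours after the site knew of it, when 24 hours is achievable. A Grade 4 event that is not an SAE may wait 48 hours before an Investigator hears of it.

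The 72 hours rests on four assumptions: the caller is not the Principal Investigator or a sub-Investigator; the caller's awareness is not treated as the Investigator's through delegation; both limits are used in full; and no manual outside these documents sets a shorter one. The documents do not allow an estimate of how often these would coincide. The change is worth making because it is a cheap safety improvement; it has no bearing on the trial's statistical conclusions.

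**What to change.** Two amendments are needed.

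1. In 10.1.3, require staff to pass Grade 4 events, and any event of whatever grade that may meet the SAE definition, to the Principal Investigator or a sub-Investigator immediately and on the same day. Keep the 48 hours for non-serious Grade 3 events.
2. In 13.1.6, count the 24 hours from awareness of the event by any member of the site staff.

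The second caps SAE reporting at 24 h however the site hears of the event. The first is what brings forward the Investigator's own review, and it alone covers Grade 4 events that are not SAEs.

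The cost is two sentences of protocol wording, a line of site training, and some extra calls to an Investigator who is already on call. If the Study Procedures Manual already contains these rules, the protocol should be brought into line with it.

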#### **10.1.4 Surveillance for Respiratory Illness**

From Day 14 following randomization and vaccination, passive and active surveillance will be performed until the end of the end of the surveillance period:

- Passive surveillance: subjects will be instructed to contact the clinical site within 24 hours in case of any new or worsening respiratory illness as defined in Section 10.2.1;
- Active surveillance: subjects will be contacted a minimum of three times per week. At least one of these contacts each week will be through a scripted telephone call, with the remaining contacts via text messaging; a higher proportion of telephone contacts may be used if deemed appropriate by the clinic site (e.g. difficulty in obtaining responses via text messaging).

Note: An episode of respiratory illness is considered to extend from the first day of the first symptom to the last day of the last symptom. In most cases, a new episode can only begin after resolution of all symptoms of the previous episode, with a separation of a seven-day symptom-free interval between episodes. However, some degree of site investigator discretion will be permitted in defining new episodes (e.g. a non-productive cough and fatigue persisting for ten days from one episode, with a new onset of myalgia, headache, and sore throat would constitute the onset of a valid new episode).

If a subject reports a new or worsening respiratory illness:

- Collect information regarding the respiratory illness, including all applicable symptoms and the onset date:
  - The onset date is defined as the first date when one or more of the qualifying symptoms (see above) occurred and persisted for at least 12 hours;
  - Symptoms collected should also include the presence or absence of concurrent systemic symptoms (i.e. fever, feverishness [feeling of warmth], chills [shivering], tiredness [fatigue], headache, myalgia [muscle aches], nausea, vomiting, or diarrhea);
- Collect information on any associated concomitant medication use;

---

Confidential Information

- Schedule a time when the subject can return to the clinic site for the collection of NP swabs. The NP swabs are to be collected within 36 hours (preferably within 24 hours) after reporting of the respiratory symptoms;
- Respiratory illnesses that start on or after Day 14 will be followed up for 30 days after the illness start date, including occurrences of any of the following in association with any respiratory illness: pneumonia (clinical diagnosis), new onset or exacerbations of pre-existing cardio-respiratory conditions, hospitalizations, emergency room visits, and non-routine medical office visits, as well as the diagnoses associated with those instances. This follow-up will be conducted via the planned active surveillance contacts (telephone and text messaging). Information from more than 30 days from respiratory illness onset does not need to be collected. As part of this follow up, the following information will be needed:
  - Collect any new information regarding the evolution of the respiratory illness, including symptoms and any associated concomitant medication use;
  - Collect data regarding the end date (if resolved). The end date is defined as the date on which the last symptom resolved;
  - Collect information regarding disease burden and health care information:
    - Document whether the illness required consultation at a clinic or with a general practitioner or family physician and if so, how many consultations;
    - Document whether the illness required consultation at an emergency department and if so, how many consultations;
    - Document whether the illness required hospitalization and if so, for how many days;
    - Document any other medical interventions associated with the illness;
    - Document whether the illness resulted in missed work days and if so, how many;
    - Document any disease sequelae (including long-term);
  - Ask subjects if they have any ILI symptoms, as defined in Section 10.2.1;
  - Ensure subjects have the reminder aid listing the symptoms of ILI and contact information for the study site.

In case a subject cannot be reached via phone, he/she may be contacted by text message or via email (if these contacts are available). However, other than for planned text message contacts, the phone should be the initial and preferred means of communication.

### 10.1.5 Day 21

For all subjects a safety follow-up will be performed on or shortly after Day 21 (- 2/+ 3 days):

- Review the subject's safety data and ensure all updates on concomitant medication usage and any changes in the subject's health (AEs, SAEs, or NOCDs) are recorded appropriately;

- Advise the subjects to immediately contact the Investigator or his/her designee, in the event of any AE that requires a visit to an emergency room and/or hospitalization;
- Remind the subjects of their next phone contact.

Note: This safety follow-up will be performed during one of the surveillance telephone contacts either on or shortly after Day 21. For the subset of subjects participating in the CMI and humoral immunity assessment, this follow-up can be done during the Day 21 visit.

The following procedures will be performed during the Day 21 (- 2/+ 3 days) visit for the subset of 400 subjects included in the immunogenicity analyses:

- Collect blood samples for CMI, HI, MN, and SRH assessments and prepare and store these samples until shipment to the analytical laboratory;
- Perform Day 21 safety follow-up (as described above) if it is to be done during this visit.

Note: This visit might replace one of the phone contacts planned for that week.

